- 28. Unresolved toxicity higher than NCI-CTCAE V.5.0 Grade 1 attributed to any prior therapy/procedure excluding alopecia, hypothyroidism and oxaliplatin induced neurotoxicity ≤ Grade 2
- 29. Concomitant participation or participation within the last 30 days in another clinical trial
- 30. Systemic anticancer therapy during this trial or within 4 weeks before randomization
- 31. Concomitant intake of St. John's wort
- 32. Live attenuated vaccines are prohibited 10 days before the treatment, during the treatment and 6 months after the termination of treatment
- 33. History of gastrointestinal fistula or perforation
- 34. Previous or concurrent cancer that is distinct in primary site or histology from colorectal cancer within 5 years prior to study inclusion, except for curatively treated cervical cancer in situ, non-melanoma skin cancer and superficial

	bladder tumors [Ta (non invasive tumor), Tis (carcinoma in situ) and T1 (lamina propria invasion)].
STUDY PRODUCT OR MEDICAL DEVICE	REGORAFENIB IRINOTECAN
ENROLLMENT PROCEDURE	Pre-treated patients with mCRC and wt or mutated RAS status Randomisation 1 :1 Genotype A/A of cyclin D1 (25% of patients) Arm A: REGIRI (irinotecan + regorafenib) Arm B: Stivarga® (Regorafenib)
TREATMENT OR SURGERY MODALITIES	Experimental arm: REGIRI (arm A) -Irinotecan will be administered every 15 days. -1st cycle: Irinotecan will be administered at the dose of 120 mg/m² on D1 by a IV perfusion over 90 minutes. -2nd cycle: if no diarrheas grade > 1 and any other toxicities grade > 2 then the Irinotecan dose will be at 150 mg/m² and administered on D1 by IV infusion over 90 minutes. -From the third cycle: if no diarrheas grade > 1 and any other toxicity grade > 2 then the Irinotecan dose will be at 180 mg/m² and administered on D1 by IV infusion over 90 minutes. D1=D15 -Regorafenib will be given orally at a dose of 160 mg, once daily during on days 2–8 and 16–22 of each cycle, D1 = D28 → A chemotherapy course = 15 days, 1 cycle = 4 weeks Control arm: STIVARGA® (Regorafenib) (arm B) -Regorafenib will be given orally at a dose of 160 mg once daily over 3 weeks followed by 1 week off, D1=D28. 1 cycle = 4 weeks

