6.1 Experimental treatment or procedures

Experimental arm: REGIRI (arm A)

[figure not shown]

Figure 1: REGIRI regimen

The treatment schedule will be as follows:

- Starting on days 1 and 15 of each 28-day cycle, all patients will receive irinotecan as an intravenous infusion over a 90 minute period.

The initial dose of irinotecan will be 120 mg/m².

The dose for the second infusion of irinotecan will be 150 mg/m² over 90 minutes if no diarrhea of grade >1 NCI-CTCAE V 5.0 grading or others toxicities of grade >2 occur.

The dose for the third and subsequent infusions of irinotecan will be 180 mg/m² over 90 minutes under the same conditions as for the 2nd infusion.

- -On days 2–8 and 16–22 of each cycle, all patients will receive Regorafenib 160 mg orally once daily.
- -A chemotherapy course = 15 days, 1 cycle = 4 weeks

Control arm: Stivarga® (Regorafenib) (arm B)

-Regorafenib will be given orally at a dose of 160 mg once daily over 3 weeks then one week off.

1 cycle = 4 weeks

[figure not shown]

Figure 2: Regorafenib schedule

The following products will be used in the study:

- Regorafenib, 40 mg tablets
- Irinotecan, 180 mg/m² IV (20 mg/ml)

ARM A: REGIRI (Regorafenib + Irinotecan)

Irinotecan

See manufacturer's product information (Appendix 8).

Irinotecan will be prescribed by each center and used in its marketed form.

The irinotecan will be diluted in a 5 % glucose solution or a 0.9% sodium chloride solution. The irinotecan will be delivered over 90 minutes as an intravenous infusion.

Regorafenib

For Packaging, List of excipients and Storage: See Investigator's brochure (Appendix 8).

Regorafenib® will be provided by Sponsor as tablets of 40 mg.

The investigational product(s) label will bear sponsor's name, address and telephone number, the EudraCT number, product name, dosage form and strength, quantity of investigational product par container, batch number, expiration date, dosing instructions, required storage conditions and required caution statements and/or regulatory statements as applicable.

Protocole NEXT-REGIRI -Version 6.0 du 09/11/2023

Page 39 sur 86

Receipt, distribution, return and destruction (if any) of the study drug must be properly documented.

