6.3 Dose modification and Dose delay

ARM A: REGIRI

Regorafenib: Dosage changes should be made in 40 mg increments (1 tablet). The recommended daily dose of Regorafenib is 160 mg.

Dose reductions of Regorafenib	
1 st reduction: 120 mg	
2 nd reduction: 80 mg	

Table a*

Digestive toxicity: Diarrhea

A symptomatic treatment of the diarrhea occurring more than 24 hours after the irinotecan administration is possible by diosmectite (Smecta®), 1 sachet/8h and loperamide (Imodium®), 2 capsules/8h until 24 hours after the last stool which is loose or watery. If, in spite of this treatment, the diarrhea is not under control in the first 24 hours then fluoroquinolones as antibiotics will be orally given during 7 days.

In case of diarrhea > grade 1, the patient will receive during the next courses of treatment a prophylactic treatment by sucralfate (Keal®) 1 sachet / 6 h et Ercefuryl® 200 at a rate of 3 capsules/24 h.

Table 1: Action and dose modification during the administration of Irinotecan and Regorafenib after the first course of treatment in case of diarrhea

Protocole NEXT-REGIRI -Version 6.0 du 09/11/2023

Page **41** sur **86**

Grade	During the course of treatment	dose at the next course of treatment
Grade 1	NA	Irinotecan at 150 mg/m². Regorafenib at 160 mg per day + prophylactic treatment
Grade 2	Interrupt irinotecan until diarrhea resolves to Grade ≤ 1	Irinotecan at 120 mg/m². Regorafenib at 160 mg per day + prophylactic treatment
Grade 3	Interrupt irinotecan until diarrhea resolves to Grade ≤ 1	Irinotecan at 120 mg/m² and Regorafenib at 120 mg per day
Grade 4	Discontinue treatment permanently	Discontinue treatment permanently

Table 2: Action and dose modification during the administration of Irinotecan and Regorafenib after the second course in case of diarrhea

Grade	During the course of	Dose at the third course of	
Grade	treatment	treatment	
		Dose-escalation of irinotecan is	
Grade 1	NA	permitted. Regorafenib at 160	
Grade I	INA	mg per day	
		+ prophylactic treatment	
		Dose-escalation of irinotecan is	
Condo 2	Interrupt irinotecan until diarrhea resolves to Grade	not permitted. Regorafenib at	
Grade 2	≤ 1	160 mg per day	
		+ prophylactic treatment	
	1st accurrance: Interrupt	1st occurrence: Decrease	
Grade 3	1st occurrence: Interrupt irinotecan until diarrhea	Irinotecan to 120 mg/m².	
	resolves to Grade ≤ 1	Regorafenib to 160 mg per day	

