	2 nd occurrence: Interrupt irinotecan until diarrhea resolves to Grade ≤ 1	2 nd occurrence: Irinotecan dose is not changed at 120 mg/m² and decrease Regorafenib to 120 mg per day
	3rd occurence : Discontinue treatment permanently	3rd occurence : Discontinue treatment permanently
Grade 4	Discontinue treatment permanently	Discontinue treatment permanently

Table 3: Action and dose modification during the administration of Irinotecan and Regorafenib after the third course and beyond in case of diarrhea

	Grade	During the course of treatment	Dose at the third course of treatment
Grade 1-2		Interrupt irinotecan until diarrhea resolves to Grade ≤ 1	No dose modification + prophylactic treatment
Grade 3	Patients having	 1st occurrence: Interrupt irinotecan until diarrhea resolves to Grade ≤ 1 2nd occurrence: Interrupt irinotecan until diarrhea resolves to Grade ≤ 1 	1st occurrence: Decrease Irinotecan to 150 mg/m². Regorafenib to 160 mg per day 2nd occurrence: Decrease Irinotecan to 120 mg/m². Regorafenib to 160 mg per day
	received the irinotecan dose of 180 mg/m2	3 rd occurence : Interrupt irinotecan until diarrhea resolves to Grade ≤ 1	3 rd occurrence: Irinotecan is not changed at 120 mg/m² and decrease Regorafenib to 120 mg per day

		4th occurence : Discontinue treatment permanently	4th occurrence: Discontinue treatment permanently
		1 st occurrence: Interrupt irinotecan until diarrhea resolves to Grade ≤ 1	1st occurrence: Decrease Irinotecan to 120 mg/m². Regorafenib to 160 mg per day
	Patients having received the irinotecan dose of 150 mg/m²	2 nd occurrence: Interrupt irinotecan until diarrhea resolves to Grade ≤ 1	2 nd occurrence: Irinotecan is not changed at 120 mg/m² and decrease Regorafenib to 120 mg per day
	3rd occurence : Discontinue treatment permanently	3rd occurence : Discontinue treatment permanently	
	Patients having received the irinotecan dose of 120 mg/m²	1st occurrence: Interrupt irinotecan until diarrhea resolves to Grade ≤ 1	1st occurrence: Irinotecan is not changed at 120 mg/m² and decrease Regorafenib to 120 mg per day
		2nd occurrence: Discontinue treatment permanently	2nd occurrence: Discontinue treatment permanently
Grade 4		Discontinue treatment permanently	Discontinue treatment permanently

Hematologic toxicity

Table 4: Action and dose modification during the administration of Irinotecan in case of hematologic toxicity

CBC at D15	Delayed Treatment	Decrease the dose for the next courses of treatment

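### Irinotecan 180 mg/m² from the third infusion depends on toxicity grade only, not on the dose last received, so a patient held at 120 has either an unplanned 50% step or no stated third dose

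*Combined protocol and SAP*

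**What the plan says.** Section 6.1 starts irinotecan at 120 mg/m². The second infusion is 150 mg/m² "if no diarrhea of grade >1 NCI-CTCAE V 5.0 grading or others toxicities of grade >2 occur". What comes after that is fixed in one further sentence: "third and subsequent infusions of irinotecan will be 180 mg/m² over 90 minutes under the same conditions as for the 2nd infusion". The synopsis has the same rule, though it counts in cycles where section 6.1 counts in infusions: "From the third cycle: if no diarrheas grade > 1 and any other toxicity grade > 2 then the Irinotecan dose" is 180 mg/m².

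Section 6.3 then gives separate diarrhoea tables by course:

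- **Table 1 (after course 1).** Grade 2: "Irinotecan at 120 mg/m². Regorafenib at 160 mg per day + prophylactic treatment". Grade 3: "Irinotecan at 120 mg/m² and Regorafenib at 120 mg per day". The column heading limits both entries to the next course.
- **Table 2 (after course 2).** Grade 1: "Dose-escalation of irinotecan is" permitted, with no dose named. Grade 2: escalation is not permitted. Grade 3, first occurrence: irinotecan goes down to 120.
- **Table 3 (course 3 onward).** Grade 3 is managed by the dose already received. For patients at 180 the first step is "1st occurrence: Decrease Irinotecan to 150 mg/m². Regorafenib to 160 mg per day"; there are further tiers headed "Patients having received the irinotecan dose of 150 mg/m²" and, likewise, 120.

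Figure 1, which shows the REGIRI regimen, is not reproduced in the text available for this review.

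**The concern.** The planned escalation has three levels, and each rise is meant to follow tolerance of the level below. The rule for 180, however, tests only whether toxicity occurred. It does not ask whether the patient has had 150. The patients for whom this matters are those held at 120 because they had grade 2 or 3 diarrhoea on the first infusion.

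Two things are at stake. One is safety: a patient who has just shown intolerance at 120 could receive 180 after one clean course. The other is consistency: a site that follows section 6.1 literally gives 180, a site that thinks in steps gives 150, and a site that reads the condition cumulatively may stay at 120. Similar patients could then get different doses in the experimental arm.

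**Working it through.** The plan states no figure to reproduce here. The check traces the dosing rule for one patient and compares step sizes.

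**Inputs.** Irinotecan levels 120, 150 and 180 mg/m² (section 6.1); the hold at 120 after grade 2 or 3 diarrhoea (section 6.3, Table 1); 39 patients per arm (section 9.1).

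**Planned path, no toxicity.** 120 to 150 to 180.
- 150/120 = 1.25, a rise of 25%.
- 180/150 = 1.20, a rise of 20%.

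**Path for a patient held after course 1.**
1. Infusion 1 at 120; grade 2 or 3 diarrhoea follows.
2. Table 1 sets infusion 2 at 120. It says nothing about infusion 3.
3. Suppose course 2 is free of toxicity. Table 2 starts at grade 1 diarrhoea, so it is not triggered, and no other table in section 6.3 applies.
4. Only section 6.1 and the synopsis remain. Read for the preceding course alone, their conditions are met, so infusion 3 is 180.
- 180/120 = 1.50, a rise of 50% (60 mg/m²) in one step.

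**The alternative reading.** The condition in section 6.1 has no time window. If it means that no such toxicity has ever occurred, this patient fails it. Section 6.1 then gives no 180, Table 1 has run out, and the third dose is unstated. Table 2 favours the per-course reading, because it decides on escalation from the diarrhoea seen in the second course.

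**Does Table 2 settle it?** No, for three reasons.
- Its grade 1 row permits escalation without naming a target, whatever happened in course 1. A patient at 120 could go to 150 or to 180.
- Its grade 3 row starts with a decrease to 120, which presumes that the patient was at 150.
- Its grade 1 row gives regorafenib 160 mg per day, although Table 1 may have cut it to 120 after grade 3 diarrhoea. The table does not track earlier holds.

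**With a one-level limit.** The held patient goes 120, 120, 150 (+25%), 180 (+20%).

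**How many patients.** The documents give no rate of holds after course 1. Purely for scale, and as an assumption, rates of 5% to 20% would give 0.05 × 39 = 1.95 to 0.20 × 39 = 7.8, so about 2 to 8 REGIRI patients held. Fewer would then have a clean course 2.

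**The case against.** The best case on the other side has three parts.

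**The surrounding text points to stepwise dosing.** Table 4 reduces by one dose level, the nadir rule drops to the next lower dose, and Table 3 foresees patients still at 120 or 150 and leaves the dose unchanged after grade 1 or 2 diarrhoea. Table 2 only permits escalation after grade 1, so 150 is open to the investigator. Figure 1 may also show the steps. This is fair as evidence of intent. But no visible sentence requires 150 before 180, and with no toxicity in course 2 none of these provisions applies.

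**Safeguards exist.** After diarrhoea above grade 1, section 6.3 adds sucralfate and Ercefuryl prophylaxis for the next courses. Grade 3 in course 1 also cuts regorafenib to 120 mg at the next course. Toxicity must be back to grade 1 or lower before irinotecan is given, grade 4 diarrhoea ends treatment, arm A has a nurse call on day 22 of cycles 1 and 2, and the safety committee reviews the first two months of treatment after twenty arm A patients (section 10.3). All of this limits the harm. None of it sets the irinotecan dose.

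**180 mg/m² is not an unusual dose.** Section 1 cites a phase Ib trial that combined FOLFIRI at that irinotecan dose with regorafenib 160 mg and reports no reduced tolerability despite higher SN-38 exposure. All patients here have had irinotecan before. This stands: a 50% step is not in itself evidence of danger.

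A reader might also infer that a patient reduced under Table 3 may return to 180 after one clean course. The documents do not support that as the natural reading. Table 3's descending ladder and dose tiers, Table 4's reference to courses in the plural, and the nadir rule all imply that reductions last, although no sentence says so.

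**Conclusion.** The gap is real and worth closing. Section 6.1 and the synopsis tie 180 mg/m² to toxicity grade alone. For a patient held at 120 under Table 1 with a toxicity-free course 2, the per-course reading gives +50% in one step, and the cumulative reading gives no stated third dose. Neither is acceptable in a dosing rule, and the first falls on patients who have just had grade 2 or 3 diarrhoea.

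A reader might infer that the protocol plainly orders the jump to 180 for every held patient. It does not: the condition has no time window, and Table 2 leaves the dose open after grade 1 and forbids escalation after grade 2.

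The conclusion assumes that Figure 1 contains no step limit. The number affected cannot be taken from the documents and is probably small. Sample size, error rates and the planned analyses are unaffected.

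**What to change.** Amend section 6.1, the synopsis and Table 2 to say:

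1. Irinotecan rises by at most one level (120 to 150 to 180 mg/m²) from the dose last received, and only if the preceding course met the toxicity conditions. This covers patients held at 120 under Table 1, who may reach 150 and then 180 after clean courses.
2. A dose reduced under Tables 2 to 4 or the nadir rule is not re-escalated.
3. Where sections 6.1 and 6.3 differ, section 6.3 prevails.

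The cost is a wording amendment and a memo to sites. If the change is judged substantial, section 12.6 requires submission to ANSM and/or the CPP. A few patients will reach 180 one course later. No extra patients, visits or procedures are needed.

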6.2 Expected Toxicities

The expected adverse events of Irinotecan, and Regorafenib are described in the respective Summaries of Product Characteristics (SmPC). Refer to the latest current version on the public drug database website (Appendix 8) for:

- Stivarga® in the Regorafenib alone arm
- Irinotecan in the REGIRI arm

Refer to the latest investigator's brochure for Regorafenib in the REGIRI arm.

6.3 Dose modification and Dose delay

ARM A: REGIRI

Regorafenib: Dosage changes should be made in 40 mg increments (1 tablet). The recommended daily dose of Regorafenib is 160 mg.

Dose reductions of Regorafenib	
1 st reduction: 120 mg	
2 nd reduction: 80 mg	

Table a*

Digestive toxicity: Diarrhea

A symptomatic treatment of the diarrhea occurring more than 24 hours after the irinotecan administration is possible by diosmectite (Smecta®), 1 sachet/8h and loperamide (Imodium®), 2 capsules/8h until 24 hours after the last stool which is loose or watery. If, in spite of this treatment, the diarrhea is not under control in the first 24 hours then fluoroquinolones as antibiotics will be orally given during 7 days.

In case of diarrhea > grade 1, the patient will receive during the next courses of treatment a prophylactic treatment by sucralfate (Keal®) 1 sachet / 6 h et Ercefuryl® 200 at a rate of 3 capsules/24 h.

Table 1: Action and dose modification during the administration of Irinotecan and Regorafenib after the first course of treatment in case of diarrhea

Protocole NEXT-REGIRI -Version 6.0 du 09/11/2023

Page **41** sur **86**

Grade	During the course of treatment	dose at the next course of treatment
Grade 1	NA	Irinotecan at 150 mg/m². Regorafenib at 160 mg per day + prophylactic treatment
Grade 2	Interrupt irinotecan until diarrhea resolves to Grade ≤ 1	Irinotecan at 120 mg/m². Regorafenib at 160 mg per day + prophylactic treatment
Grade 3	Interrupt irinotecan until diarrhea resolves to Grade ≤ 1	Irinotecan at 120 mg/m² and Regorafenib at 120 mg per day
Grade 4	Discontinue treatment permanently	Discontinue treatment permanently

Table 2: Action and dose modification during the administration of Irinotecan and Regorafenib after the second course in case of diarrhea

Grade	During the course of	Dose at the third course of	
Grade	treatment	treatment	
		Dose-escalation of irinotecan is	
Grade 1	NA	permitted. Regorafenib at 160	
Grade I	INA	mg per day	
		+ prophylactic treatment	
		Dose-escalation of irinotecan is	
Condo 2	Interrupt irinotecan until diarrhea resolves to Grade	not permitted. Regorafenib at	
Grade 2	≤ 1	160 mg per day	
		+ prophylactic treatment	
	1st accurrance: Interrupt	1st occurrence: Decrease	
Grade 3	1st occurrence: Interrupt irinotecan until diarrhea	Irinotecan to 120 mg/m².	
	resolves to Grade ≤ 1	Regorafenib to 160 mg per day	

	2 nd occurrence: Interrupt irinotecan until diarrhea resolves to Grade ≤ 1	2 nd occurrence: Irinotecan dose is not changed at 120 mg/m² and decrease Regorafenib to 120 mg per day
	3rd occurence : Discontinue treatment permanently	3rd occurence : Discontinue treatment permanently
Grade 4	Discontinue treatment permanently	Discontinue treatment permanently

Table 3: Action and dose modification during the administration of Irinotecan and Regorafenib after the third course and beyond in case of diarrhea

	Grade	During the course of treatment	Dose at the third course of treatment
Grade 1-2		Interrupt irinotecan until diarrhea resolves to Grade ≤ 1	No dose modification + prophylactic treatment
Grade 3	Patients having	 1st occurrence: Interrupt irinotecan until diarrhea resolves to Grade ≤ 1 2nd occurrence: Interrupt irinotecan until diarrhea resolves to Grade ≤ 1 	1st occurrence: Decrease Irinotecan to 150 mg/m². Regorafenib to 160 mg per day 2nd occurrence: Decrease Irinotecan to 120 mg/m². Regorafenib to 160 mg per day
	received the irinotecan dose of 180 mg/m2	3 rd occurence : Interrupt irinotecan until diarrhea resolves to Grade ≤ 1	3 rd occurrence: Irinotecan is not changed at 120 mg/m² and decrease Regorafenib to 120 mg per day

		4th occurence : Discontinue treatment permanently	4th occurrence: Discontinue treatment permanently
		1 st occurrence: Interrupt irinotecan until diarrhea resolves to Grade ≤ 1	1st occurrence: Decrease Irinotecan to 120 mg/m². Regorafenib to 160 mg per day
	Patients having received the irinotecan dose of 150 mg/m²	2 nd occurrence: Interrupt irinotecan until diarrhea resolves to Grade ≤ 1	2 nd occurrence: Irinotecan is not changed at 120 mg/m² and decrease Regorafenib to 120 mg per day
	3rd occurence : Discontinue treatment permanently	3rd occurence : Discontinue treatment permanently	
	Patients having received the irinotecan dose of 120 mg/m²	1st occurrence: Interrupt irinotecan until diarrhea resolves to Grade ≤ 1	1st occurrence: Irinotecan is not changed at 120 mg/m² and decrease Regorafenib to 120 mg per day
		2nd occurrence: Discontinue treatment permanently	2nd occurrence: Discontinue treatment permanently
Grade 4		Discontinue treatment permanently	Discontinue treatment permanently

Hematologic toxicity

Table 4: Action and dose modification during the administration of Irinotecan in case of hematologic toxicity

CBC at D15	Delayed Treatment	Decrease the dose for the next courses of treatment
ANC < 1500/mm ³	J21*	No dose modification + G-CSF

Protocole NEXT-REGIRI -Version 6.0 du 09/11/2023

Page **44** sur **86**

and Platelets > 100 000/mm ³		
Platelets < 100 000/mm ³	121*	Padusa by 1 dosa laval
Whatever the number of ANC	JZ I"	Reduce by 1 dose level

^{*} or until 28th day as needed (maximum)

Modalities of Reintroduction of treatment : ANC \geq 1500/mm³ and Platelets \geq 100 000/mm³ If the Platelets and/or ANC values are not correct at D28, the patient will discontinue permanently the study treatment.

At the time of Nadir

In the case of a grade 4 neutropenia, whatever the duration or complication i.e by an infection or fever > 38°5, the G-CSF will be administered at the next course of treatment. If the same toxicity continues with G-CSF then the irinotecan dose will be reduced at the dose immediately inferior. If there is a third occurrence of this toxicity, the patient will permanently discontinue the study treatment.

Table 5: Action and dose modification during the administration of Regorafenib in case of hematological toxicity

Hematological toxicity (Modification dose/delay for Regorafenib)			
Grade	Treatment delay	Dose modification	
Grade 0-2	No delay in Regorafenib	No modification dose	
Grade 0-2	treatment	No modification dose	
Grade 3	No delay in Regorafenib	Reduce by 1 dose levelbc	
Grade 3	treatment	heduce by Tuose level	
	Interrupt Regorafenib		
Grade 4	until hematologic	Reduce by 1 dose level ^{bc}	
	toxicity resolves to	heduce by Tuose level	
	Grade ≤ 2ª		

a If no recovery within 30 days, the treatment will be permanently discontinued.

- b If more than 2 dose reductions are necessary, the treatment will be permanently discontinued.
- c Cf table a.

Table 6: Action and dose modification during the administration of Regorafenib in case of non-hematologic toxicity

Non-hematological toxicity (dose modification/delay for Regorafenib) (except hand-foot skin reaction, hypertension, liver function test abnormalities and diarrhea)^a

Grade	Treatment delay	Dose modification
Grade 0-2	No delay in Regorafenib treatment	No dose modification
Grade 3	Interrupt Regorafenib until non hematologic toxicity resolves to Grade ≤ 2 ^b	Reduce by 1 dose level ^{cd}
Grade 4	Discontinue treatment permanently	Discontinue treatment permanently

- a In the absence of nausea/vomiting prophylaxis and diarrhea not treated.
- b If more than 2 dose reductions are necessary, the treatment will be permanently discontinued.
- c If no recovery within 30 days, the treatment will be permanently discontinued.
- d Cf table a.

Table 7: Delay and dose modification during the administration of Regorafenib in case of hand-foot skin reaction

Skin Toxicity Grade	Occurrence	Suggested Dose Modification
Grade 1: Numbness,	Any	Maintain dose level and institute immediately
dysesthesia, paraesthesia,		supportive measures for symptomatic relief
tingling, painless swelling,		
erythema or discomfort of		
the hands or feet which		
does not		
disrupt the patient's normal		
activities		

Protocole NEXT-REGIRI -Version 6.0 du 09/11/2023

Page 46 sur 86

Grade 2: Painful erythema	1st	Decreasing dose by one dose level ^a and
and swelling of the hands or	occurrence	institute immediately supportive measures.
feet and/or discomfort		If no improvement , interrupt therapy for a
which affects the patient's		minimum of 7 days, until toxicity resolves to
normal activities		Grade 0-1 ^{b.}
	No	Interrupt Regorafenib until toxicity resolves to
	improvement	Grade 0-1. When resuming treatment, treat at
	within 7 days	reduced dose levelab
	or	
	2nd	
	occurrence	
	3rd	Interrupt Regorafenib until toxicity resolves to
	occurrence	Grade 0-1. When resuming treatment, decrease
		dose by one additional dose levela b c
	4th	Discontinue treatment permanently
	occurrence	
Grade 3: Moist	1st	Institute supportive measures immediately.
desquamation,	occurrence	Interrupt therapy for a minimum of 7 days until
ulceration, blistering or		toxicity resolves to Grade 0-1. When resuming
severe pain of the hands or		treatment, decrease dose by one dose levelab
feet, or severe discomfort	2nd	Institute supportive measures immediately.
that causes the patient to	occurrence	Interrupt therapy for a minimum of 7 days until
be unable to work or		toxicity resolves to Grade 0-1. When resuming
perform activities of daily		treatment, decrease dose by one dose level ^{a b c}
living.	3rd	Discontinue treatment permanently
	occurrence	
a Cf table a		
1 16 1 16 1 16	. 4 (1)	

b If toxicity returns to Grade 0-1 after dose reduction, dose re-escalation is permitted at the discretion of the investigator

c Subjects requiring > 2 dose reductions should discontinue treatment

Suggestions:

Control of calluses

Before initiating treatment with regorafenib:

Protocole NEXT-REGIRI -Version 6.0 du 09/11/2023

Page **47** sur **86**

Réf interne ICM : ICM-ENR-432 Version : 001 Date d'application : 24/05/2017

- Check condition of hands and feet
- Suggest a manicure/pedicure, when indicated
- Recommend pumice stone use for callus or 'rough spot' removal.

During regorafenib treatment:

- Avoid pressure points
- Avoid items that rub, pinch or create friction

Use of creams

Apply non-urea based creams liberally, e.g.,

- Cetaphil
- Aveeno
- Norwegian Formula
- Eucerin

Keratolytic Creams: Use sparingly and only to affected (hyperkeratotic) areas

- Urea-based creams
- Salicylic acid 6%

Alpha Hydroxy Acids (AHA) based creams

- Approximately 5-8% provide gentle chemical exfoliation
- Apply liberally two times each day

Topical analgesics like lidocaine 2% to be considered for pain control (114)

Topical corticosteroids should be considered for subjects with Grade 2 or 3 hand-foot skin reaction (114). Avoid systemic steroids.

Cushions

Protect tender areas

Use socks/gloves to cover moisturizing creams

- Wear well-padded footwear
- Use insole cushions or inserts (e.g., silicon, gel)
- Foot soaks with tepid water and Epsom salts

Table 8: Management of treatment-emergent hypertension

NCI-CTCAE V. 5.0 grade	Definition	Antihypertensive therapy	Regorafenib dosing
1	Prehypertension (systolic BP 120 - 139 mmHg or diastolic BP 80 - 89 mmHg)	None	Continue regorafenib Consider increased BP monitoring
2	Systolic BP 140 - 159 mmHg or diastolic BP 90 - 99 mmHg, OR Symptomatic increase by > 20 mmHg (diastolic) if previously within normal limits	Treat with the aim to achieve diastolic BP ≤ 90 mmHg: - If BP previously within normal limits, start antihypertensive monotherapy. - If subject already on antihypertensive medication, titrate up the dose.	If symptomatic, hold regorafenib until symptoms resolve AND diastolic BP ≤ 90 mmHg. ^a When regorafenib is restarted, continue at the same dose level.

3	Systolic BP ≥ 160 mmHg or diastolic BP ≥ 100 mmHg OR More than one drug or more intensive therapy than previously used indicated	Treat with the aim to achieve diastolic BP ≤ 90 mmHg: - Start antihypertensive medication AND/OR - Increase current	Hold regorafenib until diastolic BP ≤ 90 mm Hg, and if symptomatic, until symptoms resolve. ^a When regorafenib is restarted, continue at the same dose level. If BP is not controlled with the addition of new or more intensive therapy,
		antihypertensive medication AND/OR - Add additional antihypertensive medications.	reduce by 1 dose level.bd If Grade 3 hypertension recurs despite dose reduction and antihypertensive therapy, reduce another dose level.cd
4	Life-threatening consequences (e.g, malignant hypertension, transient or permanent neurologic deficit, hypertensive crisis		Discontinue therapy

BP = blood pressure; NCI-CTCAE=National Cancer Institute-common terminology criteria for adverse events a Subjects requiring a delay of study treatment > 4 weeks should go off regorafenib.

Blood Pressure should be monitored weekly for the first 6 weeks of treatment. The blood pressure will be recorded by the treating physician and entered onto the e-CRF.

Any blood pressure that is out of normal range must be reported to the treating physician. Blood pressure measurements considered out of normal range are diastolic ≥100 mmHg and systolic ≥150 mmHg, or a ≥20 mmHg increase in diastolic measurement if the measurement was previously within normal limits.

b If BP remains controlled for at least one full cycle, dose re-escalation is permitted at the investigator's discretion.

c Subjects requiring > 2 dose level reductions (< 80 mg reduction) should go off regorafenib therapy.

d Cf table a.

The dose modification schedule for treatment emergent hypertension during regorafenib dosing should be followed (see [Table 11]). Subjects' blood pressure (BP) measurements will be monitored and appropriate treatment to effectively control hypertension under regorafenib treatment is strongly recommended.

The selection of anti-hypertensive medication used in this setting should be performed at the investigator's discretion, considering possible site-specific treatment guidelines. All medication should be recorded in the subjects e-CRF.

Table 9: Drug-related liver function test abnormalities

Elevations of	Occurence	Management
alanine aminotransférase (ALT)		
and/or aspartate aminotransférase (AST)		
≤ 5 times upper limit of normal (ULN) (Grade	Any	Continue treatment by
2)	occurence	Regorafenib. Control liver
		function every week until ALT
		and AST values return to < 3
		times ULN (grade 1)
		orbaseline .
> 5 times ULN AND ≤ 20 times ULN (Grade 3)	1 st occurence	Interrupt Regorafenib.
		Control ALT and AST
		values every week until
		they return to < 3 times
		ULN or baseline.
		Resuming treatment: if the
		potential benefit outweighs
		the risk of hepatic toxicity,
		reintroduce Regorafenib
		and reduce the dose of
		one tablet (40 mg) and
		control liver function every
		week for at least 4 weeks.
	2 nd	Discontinue regorafenib

Protocole NEXT-REGIRI -Version 6.0 du 09/11/2023

Page **51** sur **86**

	occurence	permanently	
> 20 times ULN (Grade 4)	Any	Discontinue regorafenib	
	occurence	permanently	
> 3 times ULN (Grade 2 or higher) with	Any	Discontinue regorafenib	
concomitant elevation of bilirubin > 2 times	occurence	permanently	
ULN		Control liver function every	
		week until resolution or	
		return to baseline	

Termination of Regorafenib:

- -In the event of gastrointestinal perforation or fistula develops
- -In the event of reversible Posterior Encephalopathy Syndrome (REPS)
- -In the event of the appearance of cardiac ischemia and/or infarction

Other toxicities

The other toxicities will have to manage symptomatically, if possible. For any toxicity grade \geq 2 at D15 except alopecia and anemia, the irinotecan will be delayed up to two weeks and the toxicity will have to be grade \leq 1 to perform the course.

ARM B: STIVARGA® (REGORAFENIB)

Dosage changes should be made in 40 mg increments (1 tablet). The recommended daily dose of Regorafenib is 160 mg.

Dose reductions of Stivarga ®
1st reduction: 120 mg
2 nd reduction: 80 mg

Table b

Table 10: Dose modification/Delay for toxicities related to study drug (except handfoot Skin reaction and hypertension)^a

NCI-CTC V5.0	Dose	Dose Modification	Dose for Subsequent Cycles
	Interruption		
Grade 0-2	Treat on time	No change	No change
Grade 3	Delay until <	Reduce 1 dose level ^c	If toxicity remains < Grade 2,

Protocole NEXT-REGIRI -Version 6.0 du 09/11/2023

Page 52 sur 86

	Grade 2 ^b		dose re-escalation can be
			considered at the discretion
			of the treating investigator.
			If dose is re-escalated and
			toxicity (Grade 3) recurs,
			institute permanent dose
			reduction.
Grade 4	Delay until <	Reduce by 1 dose level ^c .	
	Grade 2 ^b	Permanent discontinuation	
		can be considered at	
		treating investigator's	
		discretion.	

a Excludes alopecia, non-refractory nausea/vomiting, non-refractory hypersensitivity and asymptomatic laboratory abnormalities.

Table 11: Dose modifications for hand-foot skin reaction

Skin Toxicity Grade	Occurrence	Suggested Dose Modification
Grade 1: Numbness,	Any	Maintain dose level and institute immediately
dysesthesia, paraesthesia,		supportive measures for symptomatic relief
tingling, painless swelling,		
erythema or discomfort of		
the hands or feet which		
does not		
disrupt the patient's normal		
activities		
Grade 2: Painful erythema	1st	Decreasing dose by one dose level and institute
and	occurrence	immediately supportive measures.
swelling of the hands or feet		If no improvement , interrupt therapy for a
and/or discomfort which		minimum of 7 days, until toxicity resolves to
affects the patient's		Grade 0-1 ^b

b If no recovery after a 4 week delay, treatment will be permanently discontinued. c Cf table b.

normal activities	No	Interrupt Regorafenib until toxicity resolves to
	improvement	Grade 0-1. When resuming treatment, treat at
	within 7 days	reduced dose levelab
	or	
	2nd	
	occurrence	
	3rd	Interrupt Regorafenib until toxicity resolves to
	occurrence	Grade 0-1. When resuming treatment, decrease
		dose by one additional dose level ^{a b c}
	4th	Discontinue treatment permanently
	occurrence	
Grade 3: Moist	1st	Institute supportive measures immediately.
desquamation,	occurrence	Interrupt therapy for a minimum of 7 days until
ulceration, blistering or		toxicity resolves to Grade 0-1. When resuming
severe pain of the hands or		treatment, decrease dose by one dose levelab
feet, or severe discomfort	2nd	Institute supportive measures immediately.
that causes the patient to	occurrence	Interrupt therapy for a minimum of 7 days until
be unable to work or		toxicity resolves to Grade 0-1. When resuming
perform activities of daily		treatment, decrease dose by one additional
living.		dose level ^{a b c}
	3rd	Discontinue treatment permanently
	occurrence	
a Cf table b		

b If toxicity returns to Grade 0-1 after dose reduction, dose re-escalation is permitted at the discretion of the investigator

c Subjects requiring > 2 dose reductions should discontinue treatment

If no recovery after a 4 week delay, treatment will be discontinued permanently.

For subjects who require a dose reduction for Grade 2 or 3 rash or hand-foot skin reaction (HFSR), the dose of study drug may be increased to the starting dose after one full cycle of therapy has been Administered with the reduced dose without the appearance of rash or HFSR > Grade 1.

The following measurements should be considered for prevention and treatment of hand-foot skin reaction:

Termination of Stivarga®:

- -In the event of gastrointestinal perforation or fistula develops
- -In the event of reversible Posterior Encephalopathy Syndrome (REPS)
- -In the event of the appearance of cardiac ischemia and/or infarction

Suggestions:

Control of calluses

Before initiating treatment with regorafenib:

- Check condition of hands and feet
- Suggest a manicure/pedicure, when indicated
- Recommend pumice stone use for callus or 'rough spot' removal.

